1
2
3
4
5

6 **BivaliRudin for Acute Myocardial Infarction versus
7 **heparin and GPI plus Heparin Trial (BRIGHT)****

8
9

Study Protocol

10
11

12
13
14

Version: V1.03
Version date: 2012-04-09

15
16
17
18

19 **Statement: any information regarding to this trial is prohibited to be disclosed to any other**
20 **party beyond the scope specified in this protocol without prior written consent of sponsor.**

21 **Protocol Synopsis**

| | |
|------------------------|---|
| Title of study | Bivalirudin for Acute Myocardial Infarction versus heparin and GPI plus Heparin Trial (BRIGHT) |
| Sponsor | General Hospital of Shenyang Military Region |
| Principal investigator | [name] |
| Primary study center | General Hospital of Shenyang Military Region |
| Study centers | Approximately 82 centers in China |
| Time frame of study | First patient in: August, 2012 |
| | Last patient in: December, 2013 |
| Objectives | To investigate safety and efficacy of bivalirudin for patients with AMI undergoing primary PCI. |
| Study design | Prospective, multicenter, randomized, open-label, active controlled study. |
| Study medication | Bivalirudin |
| Control medications | (1) Heparin; (2) heparin plus tirofiban |
| Treatment | 
Patients were randomly assigned to receive bivalirudin alone, heparin alone, or heparin plus tirofiban in a 1:1:1 ratio.
 
(1) Bivalirudin alone arm: Bivalirudin was given before coronary angiography in the catheterization laboratory, initialized with a bolus of 0.75 mg/kg followed by infusion of 1.75 mg/kg/hr during the PCI procedure and for at least 30 minutes but no more than 4 hours after procedure. Following this mandatory infusion, a reduced dose infusion (0.2 mg/kg/hr) for up to 20 hours could be administered at physician discretion. An additional bivalirudin bolus of 0.3 mg/kg was given if the activated clotting time (ACT) five minutes after the initial bolus (measured with the Hemotec assay) was <225 seconds.
 
(2) Heparin alone arm: A bolus dose (100 U/kg) of heparin was given before coronary angiography in the catheterization laboratory. Additional heparin bolus (20U/kg) was administered if the post-bolus ACT was <225 seconds.
 
NOTE: Provisional (bailout) tirofiban use was allowed in the bivalirudin and heparin alone groups for no-reflow, slow flow, visible thrombus or other thrombotic complications. According to Chinese experts consensus, intra-coronary tirofiban should be initialized as 500-750µg, and can be repeated after 3-5min, with a total dose no more than 1500-2250µg. Intra-venous tirofiban administration should be initialized with a bolus of
 |

| | |
|--------------------|--|
| | 
10µg/kg (within 3min) and followed by a 0.15µg/kg/min infusion for 18-36 hours.
 
(3) Heparin plus tirofiban arm: Study medications were started before coronary angiography in the catheterization laboratory. Heparin 60 U/kg and tirofiban 10 µg/kg boluses (administrated within 3 min) were given followed by a 0.15 µg/kg/min tirofiban infusion for 18-36 hours. Additional heparin bolus (20U/kg) was administered if the post-bolus ACT was <200 seconds.
 |
| Study endpoints | 
Primary endpoint:
 
Net adverse clinical events (NACE) at 30 days, defined as a composite of major adverse cardiac and cerebral events (MACCE, all-cause death, re-infarction, ischemia-driven target vessel revascularization or stroke) and any bleeding events.
 |
| | 
Secondary endpoints:
 
 • NACE at 12 months; • MACCE at 30 days and 12 months; • Any bleeding events (evaluated by BARC classification) at 30 days and 12 months. |
| | 
Safety endpoints:
 
 • Stent thrombosis (definite or probable by ARC definition) at 30 days and 12 months; • Thrombocytopenia at 30 days; • Any other abnormal symptoms, signs or laboratory test results with clinical significance. |
| Number of patients | Approximately 2100 patients. |
| | 700 patients in bivalirudin arm; 700 patients in heparin arm; 700 patients in heparin plus tirofiban arm |
| Follow-up | 12 months |
| Eligible patients | Patients with AMI in whom an emergency PCI is planned |
| Inclusion criteria | 
(1) Patients aged from 18~80 years, male or female;
 
(2) AMI (STEMI or NSTEMI) patients with planned emergency PCI.
 
 •STEMI within 12 hours after symptom onset or within 12~24 hours with ongoing chest pain, continuous ST segment elevation or new left bundle block. •NSTEMI within 72 hours after symptom onset. 
(3) Staged revascularization for non-culprit vessel should be performed after 30 days.
 
(4) Antiplatelet agents (aspirin and clopidogrel, both loading and maintenance dose) are given before PCI per guidelines.
 
(5) Subjects or legal representatives voluntarily participated and signed
 |

| | |
|--------------------|---|
| | informed consent, willing to accept study medications and clinical follow-ups. |
| Exclusion criteria | 
(1) Patients not suitable for PCI; thrombolytic therapy administered before randomization; cardiogenic shock;
 
(2) Any anticoagulant (heparin/LMWH, fondaparinux, warfarin or bivalirudin) or tirofiban administered within 48 hours before randomization;
 
(3) Active or recent major bleeding or bleeding predisposition, including retinal or vitreous hemorrhage within one month, GI or urinary track hemorrhage within 3 months, intracranial hemorrhage within 6 months or cerebral infarction within 3 months;
 
(4) Patients at high risk of secondary bleeding, including active gastric ulcer, ulcerative colitis, intracranial aneurysm, etc.;
 
(5) Major surgery (including ophthalmologic operation or neurosurgery) within 1 month;
 
(6) Clinical syndrome suspicious for aortic dissection, pericarditis or endocarditis;
 
(7) Uncontrolled blood pressure (>180/110 mmHg);
 
(8) Known hemoglobin <10 g/dL or platelet count <100 × 10⁹/L;
 
(9) Aminotransferase level >3x the upper limit of normal;
 
(10) Severe renal insufficiency (eGFR<30 mL/min/1.73m²);
 
(11) History of heparin induced thrombocytopenia;
 
(12) Known allergy to study medications or device (heparin, bivalirudin, tirofiban, aspirin, clopidogrel, stainless steel, contrast medium or hirudin) or allergic constitution;
 
(13) Patient pregnant or lactating, or planned pregnant within 1 year;
 
(14) Study subjects with poor compliance judged by investigators or patient ever participated in another clinical trial and has not completed the follow-up to the primary endpoint.
 |
| Study timelines | 
Start of the study: August, 2012.
 
First patient enrolled: August, 2012
 
Last patient finished: December, 2013
 |
| Statistical method | All primary and major secondary endpoints will be analyzed both on an intent-to-treat basis (all patients analyzed as part of their assigned treatment group) and on a per protocol basis (patients analyzed as part of their assigned treatment group only if they actually received their assigned treatment). The primary statistical analyses will be by intent-to-treat. |
| Version/date | V1.03/2012-04-09 |

22

23

Table of Contents

| | |
|---|----|
| 1. Background | 7 |
| 2. Objectives | 8 |
| 3. Introduction of study drug | 8 |
| 3.1 Bivalirudin | 8 |
| 3.2 Heparin | 9 |
| 3.3 Tirofiban | 10 |
| 4. Previous clinical research | 11 |
| 5. Design, randomization and blinding | 13 |

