70 parallel-group, open-label randomized trial. Bivalirudin will be used in patients with
71 AMI undergoing an invasive primary angioplasty strategy, and approximately 2100
72 patients will be enrolled. The control therapies include heparin and heparin plus
73 tirofiban. Efficacy and safety of domestic bivalirudin will be evaluated in those
74 patients at 30 days, 6 months and 12 months after the procedure.

75 **3. Introduction of study drugs**

76 **3.1 Bivalirudin**

77 **3.1.1 Pharmacology**

78 Bivalirudin is a direct, specific, reversible inhibitor of thrombin, and its
79 anticoagulation effect is independent of antithrombin III. It inhibits thrombin
80 irrespective of whether the thrombin is free in solution or bound to fibrin, and
81 inhibits thrombin activity directly. Following cleavage at Arg3-Pro4, bivalirudin no
82 longer binds to thrombin, thus allowing thrombin to resume its pro-hemostatic
83 functions, therefore, its effects is short and reversible. *Ex vitro* study from healthy
84 participants showed that, the prothrombin time (PT), activated partial thromboplastin
85 time (APTT), and thrombin time (TT) all rose in a linear fashion with increasing
86 doses of bivalirudin. Binding of bivalirudin to free thrombin or thrombin bound to
87 fibrin is independent of platelet-derived micro-particles. The same level of
88 anticoagulation effects could be achieved in patients undergoing PCI as healthy
89 participants. Bivalirudin is administered by intravenous route, and produces a rapid
90 anticoagulant effect. The half-life of bivalirudin is 25 minutes, and patients'

91 coagulation system becomes normal 1h after cessation of treatment. There is no
92 specific antidote for bivalirudin.

93 **3.1.2 Drug interactions**

94 Bivalirudin does not bind to plasma protein or red blood cells.
95 Co-administration of bivalirudin with heparin, warfarin, or thrombolytic agents has
96 not been associated with increased risks of major bleeding events.

97 **3.1.3 Adverse reactions**

98 One of common adverse reactions of bivalirudin is bleeding, usually occurring
99 at the puncture site of the artery, or other body part. Bleeding should be highly
100 suspected when abrupt hypotension, volume loss, or other unclear symptoms occur,
101 and bivalirudin should be stopped. Other rare adverse reactions include
102 thrombocytopenia, anemia, allergy, ventricular tachycardia, chest pain, bradycardia,
103 dyspepsia, rash, back pain, headache and hypotension.

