191 clinical events) within 30 days. The results showed that anticoagulation with
192 bivalirudin alone, as compared with heparin plus glycoprotein IIb/IIIa inhibitors,
193 resulted in a reduced 30-day rate of net adverse clinical events (9.2% vs. 12.1%;
194 relative risk, 0.76; 95% confidence interval [CI] 0.63 to 0.92; P=0.005), owing to a
195 lower rate of major bleeding (4.9% vs. 8.3%; relative risk, 0.60; 95% CI, 0.46 to
196 0.77; P<0.001). Treatment with bivalirudin alone, as compared with heparin plus
197 glycoprotein IIb/IIIa inhibitors, resulted in significantly lower 30-day rates of death
198 from cardiac causes (1.8% vs. 2.9%; relative risk, 0.62; 95% CI, 0.40 to 0.95;
199 P=0.03) and death from all causes (2.1% vs. 3.1%; relative risk, 0.66; 95% CI, 0.44

200 to 1.00; P=0.047). One-year outcomes in the HORIZONS-AMI trial continued to
201 show that bivalirudin is associated with a lower rate of major bleeding (15.6% versus
202 18.3%, p=0.0001) and mortality (3.5% versus 4.8%, p=0.037). In HORIZONS-AMI,
203 there was an increased risk of acute stent thrombosis within 24 hours in the
204 bivalirudin group, which might due to delayed onset of pharmacodynamic effects of
205 clopidogrel.

206

207 **5. Study design, randomization and blinding**

208 **5.1 Study design**

209 This study is a prospective, multicenter, randomized, active controlled,
210 open-label, superiority trial.

211 **5.2 Study procedure**

212 Patients meet ALL the inclusion criteria and NONE of the exclusion criteria
213 will be randomly assigned to 3 arms after informed consent is signed. Study
214 medications will be given in the cath lab before angiography. Activated clotting time
215 (ACT) will be measured 5 min after heparin or bivalirudin administration. Repeat
216 bivalirudin or heparin bolus will be given if ACT is less than standard level
217 according to protocol. Bailout tirofiban can be used in patients allocated in the
218 bivalirudin arm or heparin arm if there is significant thrombus in the culprit vessel.
219 Patients will be visited at 30 days, 6 months and 12 months via telephone or clinic.
220 Detailed study procedures are listed in table 1.

221 **5.3 Randomization**

222 Patients meeting ALL the inclusion criteria and NONE of the exclusion criteria
223 will be enrolled. Randomization will be performed in catheterization laboratory
224 immediately after informed consent is signed, using computer-generated block

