254 vitreous hemorrhage within one month, GI or urinary track hemorrhage within 3
255 months, intracranial hemorrhage within 6 months or cerebral infarction within 3
256 months;

257 (4) Patients at high risk of secondary bleeding, including active gastric ulcer,
258 ulcerative colitis, intracranial aneurysm, etc.;

259 (5) Major surgery (including ophthalmologic operation or neurosurgery) within 1
260 month;

261 (6) Clinical syndrome suspicious for aortic dissection, pericarditis or endocarditis;

262 (7) Uncontrolled blood pressure (>180/110 mmHg);

263 (8) Known hemoglobin <10 g/dL or platelet count <100 × 10⁹/L;

-
- 264 (9) Aminotransferase level >3x the upper limit of normal;
265 10) Severe renal insufficiency (eGFR<30 mL/min/1.73m²);
266 (11) History of heparin induced thrombocytopenia;
267 (12) Known allergy to study medications or device (heparin, bivalirudin, tirofiban,
268 aspirin, clopidogrel, stainless steel, contrast medium or hirudin) or allergic
269 constitution;
270 (13) Patient pregnant or lactating, or planned pregnant within 1 year;
271 (14) Study subjects with poor compliance judged by investigators or patient ever
272 participated in another clinical trial and has not completed the follow-up to the
273 primary endpoint.

274

275 **6.4 Criteria of patient removal, treatment discontinuation and drop out**

276 **6.4.1 Criteria of removal**

277 Patient should be removed if:

- 278 • Misdiagnosis.
- 279 • Without any record of physical or laboratory test results.
- 280 • Do not meet the inclusion criteria or meet at least one exclusion criteria.

281 The reason of removal should be written down and the case report form (CRF) should
282 be preserved for audit check. Removal patients will not be included in the efficacy
283 analysis but could be included in the safety analysis if there are any records regarding
284 efficacy or safety.

285 **6.4.2 Criteria of treatment discontinuation**

286 Discontinuation of any study medication is defined as stopping experimental
287 treatment. The reason of discontinuation should be clearly noted in the original
288 medical records and CRF.

289 Treatment should be discontinued if:

- 290 • Patient withdrawal of informed consent.
- 291 • Intolerable side effects of study medications

-
- 292 • Severe allergy that cannot be relieved by anti-allergic therapy
 - 293 • Adverse events or abnormal laboratory test results indicating that
 - 294 continuation of treatment would be inappropriate.

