 - 295 • Patient suffered from severe complications which necessitated withdrawing
 - 296 study medications.
 - 297 • Major deviation of the study protocol.
 - 298 • Severe adverse event that threaten the patient’s health.

299

300 **6.4.3 Criteria for drop out**

301 All patients enrolled in the trial shall be retained until completion of follow-up.
302 Patients have the right to withdraw from the study at any time without penalty, and
303 would not lose any benefits. The reasons that patients drop out may include but are
304 not limited to:

- 305 • Severe adverse events causing termination of the study.
- 306 • Unexpected illness for which further treatment would be inappropriate.
- 307 • Lost to follow-up.
- 308 • Patient withdrew informed consent.
- 309 • Other reasons causing termination of the study.
- 310 • Poor patient compliance which might affect efficacy or safety.

311

312 If patients met the above criteria and stop participating in the study, the
313 “completion of study” page in their case reports should be completed. Investigators
314 must report to their respective ethics committees when and why patients stopped
315 participating in the study (according to the procedures specified in each test body). If
316 patient withdrawal was caused by an AE/SAE, clinical follow-up should be performed
317 until the AE/SAE is resolved or stabilized.

318

319 **7. Methods**

320 **7.1 Study medications:**

- 321 • Bivalirudin for injection : 250mg per ampoule, manufactured by Salubris

322 Pharmaceutical Co. Ltd, Shenzhen, China

323 ● Heparin Sodium injection: 100mg per ampule

324 ● Tirofiban hydrochloride Sodium Chloride Injection: 100mg per package

325

326 **7.2 Follow-up:**

327 Clinical follow-up will be performed at 30 days, 6 months and 12 months after
328 randomization.

329

330 **7.3 Treatment**

331 Patients enrolled will be randomly assigned to receive bivalirudin alone, heparin
332 alone or heparin plus tirofiban in a 1:1:1 ratio. Treatments for 3 arms are as follows:

333

334 **7.3.1 Bivalirudin alone arm:**

335 Bivalirudin is given before coronary angiography in the catheterization laboratory,
336 initialized with a bolus of 0.75 mg/kg followed by infusion of 1.75 mg/kg/hr during
337 the PCI procedure and for at least 30 minutes but no more than 4 hours after
338 procedure. Following this mandatory infusion, a reduced dose infusion (0.2 mg/kg/hr)
339 for up to 20 hours may be administered at physician discretion. An additional

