465 medical records.

466 • To ensure all errors and missing data are corrected or illustrated and signed
467 by the investigator.

468 • To ensure each therapeutic change, concomitant medication and complication
469 is recorded accurately.

470 • To ensure that all patient withdrawals or loss of follow-up are recorded in the
471 CRF.

472 • To ensure that all AEs are recorded and all SAEs are reported per standard
473 procedure.

474 • To ensure that the delivery, storage and recycling of study drugs abide to
475 regulatory requirements and are recorded.

476

477 **12. Statistical analysis**

478 BRIGHT is a prospective, multicenter, randomized, open label, active controlled
479 trial. AMI patients with planned emergency PCI will be enrolled and randomly
480 assigned to be treated with bivalirudin, heparin alone or heparin plus tirofiban.

481 Analysis for primary endpoint will be performed at the time that 30 day follow-up for
482 all subjects are completed. Analysis for secondary endpoints will be performed when
483 12-month follow-up are completed.

484 **12.1 Sample size calculation**

485 The primary endpoint is 30-day NACE, a composite of all-cause death,
486 reinfarction, ischemia driven TVR, stroke or any bleeding. Incidence of primary
487 endpoint will be compared between bivalirudin group and two control groups
488 sequentially. Only when both p values of two step tests (bivalirudin versus heparin
489 alone and bivalirudin versus heparin plus tirofiban) are less than 0.05, then the

490 conclusions of bivalirudin being superior to controls will be accepted.

491 The study hypothesis is that bivalirudin is superior to both heparin alone and
492 heparin plus tirofiban on 30-day NACE.

493 $H_0: P_B = P_C$

494 $H_1: P_B \neq P_C, \alpha = 0.05$ (two-sided)

495 P_B denotes NACE rate in the bivalirudin group, P_C NACE rate in the control group.

496 Assuming a 30-day NACE rate of 11.5% in the heparin alone group and 12.1%
497 in the heparin plus tirofiban group, allowing for 5% lost to follow-up, with a
498 two-sided alpha of 0.05, 700 patients per group would provide >90% power to
499 demonstrate a 45% reduction with bivalirudin for each comparison. Enrollment of
500 2,100 total patients (~700 per group) was therefore planned.

501

502 **12.2 Analysis populations**

503 All primary and major secondary endpoints will be analyzed both on an
504 intent-to-treat basis (all patients analyzed as part of their assigned treatment group)

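### A patient dosed and then found unsuitable for PCI at angiography can be removed from the primary analysis by staff who know the arm; separately, Sections 2 and 7.2 start the follow-up clock at different points

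*Protocol*

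**What the plan says.** **Order of events.** Protocol 5.2 states that study "medications will be given in the cath lab before angiography", and 7.3 repeats this for each arm. Under 5.4, investigators and patients know the treatment; only the clinical events committee is blinded.

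**Eligibility.** Inclusion criterion 2 asks for a planned emergency PCI, not a completed one. Exclusion 1 (synopsis and 6.3) is "Patients not suitable for PCI; thrombolytic therapy administered before randomization; cardiogenic shock". The thrombolysis item carries a time limit; the PCI item does not. Sections 5.2 and 5.3 check eligibility before randomisation.

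**Removal.** One ground for removal in 6.4.1 is "Do not meet the inclusion criteria or meet at least one exclusion criteria". Removed patients are left out of the efficacy analysis, but may enter the safety analysis if efficacy or safety records exist.

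**Analysis sets.** The synopsis and 12.2 make intention-to-treat primary and describe it as all patients in their assigned group. The ITT set in 12.2 requires the inclusion criteria, consent, study drug and some primary endpoint assessment. It does not require PCI. Only the per-protocol set requires a successful procedure.

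**Clock.** Section 2 evaluates efficacy and safety in "patients at 30 days, 6 months and 12 months after the procedure". Section 7.2 says "Clinical follow-up will be performed at 30 days, 6 months and 12 months after" randomisation. Section 8.1 says only that NACE is assessed at 30 days.

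**The concern.** Whether the coronary anatomy suits PCI is known only from the angiogram, which follows randomisation and the first dose. If that finding counts as meeting exclusion 1, then 6.4.1 takes the patient out of the efficacy analysis. The decision lies with staff who know the arm and may already have seen a bleed.

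These patients belong in a comparison of strategies that start before angiography. They can carry primary endpoint events: NACE includes any bleeding, and the bleeding definition in Appendix 1 includes CABG-related bleeding (Type 4). If removal depends on arm and outcome, the primary comparison is biased.

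The clock is a smaller, separate matter. Counted from the procedure, a bleed between bolus and PCI precedes the start of the window, and a patient without PCI has no date from which to count 30 days. Counted from randomisation, neither problem arises.

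**Working it through.** **1. The passages side by side.**
- Exclusion 1 with 5.2 and 5.3 alone is a check before randomisation.
- Section 6.4.1 acts after enrolment. It allows removed patients to have efficacy or safety records, so removal can follow treatment. It sets no cut-off and names no blinded decision-maker. The committee in Section 14 classifies events; it is given no role in eligibility.
- The synopsis and 12.2 keep all patients in their assigned group. A dosed patient removed under 6.4.1 cannot satisfy that statement.

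**2. The plan's own figure.** Section 12.1 claims "two-sided alpha of 0.05, 700 patients per group would provide >90% power to" show a 45% reduction, with control rates of 11.5% and 12.1% and 5% lost. Per arm, n = 700 × 0.95 = 665.

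Power = Φ[(d − 1.96·SE0)/SE1], where SE0 = √(2p̄(1−p̄)/n) and SE1 = √([pC(1−pC) + pB(1−pB)]/n).
- 11.5% against 0.55 × 11.5% = 6.325%: d = 0.05175, SE0 = 0.015625, SE1 = 0.015561. Power = Φ(1.36) = 91.3%.
- 12.1% against 6.655%: d = 0.05445, SE0 = 0.015987, SE1 = 0.015917. Power = Φ(1.45) = 92.7%.

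The stated power reproduces, and the point does not depend on any error in it.

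**3. Equal removal costs power only.** Let f be the assumed share of dosed patients without PCI, and use n = 665(1 − f). Power (11.5% / 12.1% control) is 90.7% / 92.2% at f = 2%, 89.9% / 91.4% at 5% and 88.2% / 89.9% at 10%.

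**4. Unequal removal biases the test.** Take 700 per arm, true NACE 11.5% in all three arms, and the pooled z-test at two-sided 0.05. Remove k patients with events from the bivalirudin arm only, so that x of 700 becomes x − k of 700 − k. Summing exact binomial probabilities gives:

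| k removed | False superiority, one comparison | Both comparisons |
|---|---|---|
| 0 | 2.5% | 0.5% |
| 3 | 4.3% | 1.1% |
| 5 | 5.9% | 1.7% |
| 10 | 12.4% | 4.8% |

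For the last column, given the bivalirudin count the two controls are independent. The conditional rejection probability is therefore squared and averaged over that count. If bivalirudin truly beat one control and only equalled the other, the joint figure would move towards the single-comparison column.

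**5. Is k = 5 plausible?** Five is 5/700 = 0.7% of an arm. At f = 3%, 0.03 × 700 = 21 patients have no PCI, with 21 × 0.115 = 2.4 expected events, fewer than five. At f = 10%, 70 patients have 8.05 expected events, so five is 62% of them. A higher event rate in these patients would make five easier to reach.

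**6. Removal of the whole group from the bivalirudin arm only** (665 per arm, control rate 11.5%, no true difference). The two-sided rejection rate stays at about 5.0% if the removed patients' NACE rate is 12%. At 20% it is 5.7% (f = 5%) and 8.3% (f = 10%). At 30% it is 8.6% and 22.0%.

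**The case against.** The best defence is that exclusion 1 is a screening check. Sections 5.2 and 5.3 put the whole list before randomisation, and other items, such as cardiogenic shock in the same line, carry no time limit either. Nobody would read those as exclusions after dosing. This stands for exclusion 1 taken alone. It does not answer 6.4.1, which applies the list after enrolment without a cut-off.

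A reader might infer that the protocol confines the primary analysis to patients who had PCI. It does not: inclusion asks for planned PCI, and the ITT set does not mention PCI. That makes the conflict with 6.4.1 sharper, because one rule keeps the patient and the other removes them.

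A reader might also infer that patients without PCI have no time zero. Section 7.2 gives every randomised patient one, so the defect is a contradiction with Section 2. Its effect on patients who have PCI should be small. Randomisation takes place in the catheterisation laboratory, the 30-day visit window is ±7 days (Table 1), and 10.2 collects adverse events from consent.

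Finally, 5.9% is not the trial's overall false-positive rate. Section 12.1 accepts superiority only if both comparisons reach p < 0.05, and the scenario removes events from one arm only. This objection stands in full.

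**Conclusion.** The point holds. Exclusion 1 read with 6.4.1 allows a dosed patient found unsuitable for PCI at angiography to leave the primary analysis by an unblinded decision, against the all-patients statement in the synopsis and 12.2. Sections 2 and 7.2 also contradict each other on the time origin.

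The size cannot be fixed from the protocol, which gives no share of patients without PCI and no event rate for them. There is bias only if removal differs by arm and the removed patients differ in event rate. On the illustration of five event patients removed from the bivalirudin arm alone, with 11.5% NACE in all arms, false superiority goes from 2.5% to 5.9% in one comparison and from about 0.5% to 1.7% for the joint claim. This is a route to bias that should be closed; it is not evidence that the result would be wrong.

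**What to change.** - **Exclusion 1** (synopsis and 6.3): limit unsuitability for PCI to grounds known before randomisation.
- **Section 6.4.1**: state that a randomised patient found unsuitable for PCI at angiography stays in the assigned arm for the primary NACE analysis, so that it agrees with the synopsis and 12.2. Changing exclusion 1 without 6.4.1 would leave the removal rule in place.
- **Section 2**: time evaluations from randomisation, as in 7.2, for NACE, MACCE and bleeding. Stent thrombosis stays timed from the index PCI, as in Appendix 1.

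A descriptive table of NACE by whether PCI was done is optional.

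The cost is wording, plus some dilution of the effect. If retained patients without PCI have the control event rate and no treatment effect (a pessimistic assumption, since they were dosed), power at 665 per arm (11.5% / 12.1% control) is 90.0% / 91.5% at a 2% share, 87.9% / 89.6% at 5% and 83.8% / 85.8% at 10%. The loss is slight at low shares and grows with the share.
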